5.2 ENROLLMENT AND RETENTION OF STUDY POPULATION

5.2.1 Recruitment Procedures

Before the start of the study, the Investigator will contact an appropriate pool of potential subjects and invite them to participate in the study. The site will ensure that any advertisements used to recruit subjects (e.g., letters, pamphlets, posters) are submitted to the Sponsor prior to submission to the IEC/IRB for approval.

5.2.2 Informed Consent Procedures

The Investigator should fully inform the Subject of all pertinent aspects of the clinical study including the written information given approval/favorable opinion by the ethics committee

(IEC/IRB). All participants should be informed to the fullest extent possible about the study, in language and terms they are able to understand.

Prior to a subject's participation in the clinical study, the written ICF should be signed, name filled in and personally dated by the subject. A copy of the signed and dated written ICF will be provided to the subject.

If new information becomes available that may be relevant to the subject's willingness to continue participation in the study, this will be communicated to him/her in a timely manner. Such information will be provided via a revised ICF or an addendum to the original ICF.

The ICF used by the investigator for obtaining the subject's informed consent must be reviewed and approved by the Sponsor prior to submission to the appropriate ethics committee (IEC/IRB) for approval/favorable opinion.

Documentation of the consent process should be recorded in the source documents.

5.2.3 Screening Criteria

There are no screening criteria other than the inclusion and exclusion criteria.

5.2.4 Inclusion Criteria

An individual must fulfill all of the following criteria in order to be eligible for study enrollment:

- I 01. Aged ≥ 65 years on the day of inclusion
- I 02. Informed consent form has been signed and dated
- I 03. Able to attend all scheduled visits and to comply with all study procedures

5.2.5 Exclusion Criteria

An individual fulfilling any of the following criteria is to be excluded from study enrollment:

- E 01. Participation at the time of study enrollment (or in the 4 weeks preceding the study vaccination) or planned participation during the present study period in another clinical study investigating a vaccine, drug, medical device, or medical procedure
- E 02. Receipt of any vaccination with live vaccines within the past 27 days preceding the study vaccination or any vaccination with inactivated vaccines within the past 6 days preceding the study vaccination, or planned receipt of any vaccine prior to V3
- E 03. Previous vaccination against influenza (in the preceding 6 months) with either the study vaccine or another vaccine
- E 04. Receipt of immune globulins, blood or blood-derived products in the past 3 months

- E 05. Known or suspected congenital or acquired immunodeficiency; or receipt of immunosuppressive therapy, such as anti-cancer chemotherapy or radiation therapy, within the preceding 6 months; or long-term systemic corticosteroid therapy (prednisone or equivalent for more than 2 consecutive weeks within the past 3 months)
- E 06. Known systemic hypersensitivity to eggs, chicken proteins, or any of the vaccine components, or history of a life-threatening reaction to the vaccine used in the study or to a vaccine containing any of the same substances
- E 07. Thrombocytopenia or bleeding disorder, contraindicating IM vaccination based on Investigator's judgment
- E 08. Deprived of freedom by an administrative or court order, or in an emergency setting, or hospitalized involuntarily
- E 09. Alcohol or substance abuse that, in the opinion of the Investigator might interfere with the study conduct or completion.
- E 10. Chronic illness that, in the opinion of the Investigator, is at a stage where it might interfere with study conduct or completion^a
- E 11. Identified as an Investigator or employee of the Investigator or study center with direct involvement in the proposed study, or identified as an immediate family member (i.e., parent, spouse, natural or adopted child) of the Investigator or employee with direct involvement in the proposed study
- E 12. Personal or family history of Guillain-Barré syndrome
- E 13. Neoplastic disease or any hematologic malignancy (except localized skin or prostate cancer that is stable at the time of vaccination in the absence of therapy and subjects who have a history of neoplastic disease and have been disease free for ≥ 5 years)
- E 14. Moderate or severe acute illness/infection (according to Investigator judgment) on the day of vaccination or febrile illness (temperature $\geq 37.5^{\circ}\text{C}$). A prospective subject should not be included in the study until the condition has resolved or the febrile event has subsided
- E 15. History of convulsions

^a Chronic illness may include, but is not limited to, asthma, cardiac disorders, renal disorders, auto-immune disorders, diabetes, psychiatric disorders or chronic infection.

If the subject has a primary physician who is not the Investigator, the site urges the subjects to contact this physician to inform him/her of the subject's participation in the study.

5.2.6 Medical History

Prior to enrollment, subjects will be assessed for pre-existing conditions and illnesses, both past and ongoing. Any such conditions will be documented in the source document. Significant

medical history (reported as diagnosis) including conditions for which the subject is or has been followed by a physician or conditions that could resume during the course of the study or lead to an SAE or to a repetitive outpatient care will be collected in the CRB. The significant medical history section of the CRB contains a core list of body systems and disorders that could be used to prompt comprehensive reporting, as well as space for the reporting of specific conditions and illnesses.

For each condition, the data collected will be limited to:

- Diagnosis (this is preferable to reporting signs and symptoms)
- Presence or absence of the condition at enrollment

The purpose of this data is to assist later in the interpretation of safety data collected during the study.

The reporting of signs and symptoms is strongly discouraged.

Dates, medications, and body systems are not to be recorded, and if the information is collected, it will not be coded.

5.2.7 Contraindications for Subsequent Vaccinations

Not applicable since only one dose of vaccine will be administered in this study.

5.2.8 Conditions for Withdrawal

Subjects will be informed that they have the right to withdraw from the study at any time. A subject may be withdrawn from the study:

- At the discretion of the Investigator or Sponsor due to safety concerns (withdrawal) without the subject's permission
- At the request of the subject (dropout)

The following will result in automatic withdrawal or exclusion of a subject from the study:

- Significant noncompliance with the protocol, based on the Investigator's judgment

The reason for a withdrawal or dropout should be clearly documented in the source documents and on the CRB.

The Investigator must determine whether voluntary withdrawal is due to safety concerns (in which case, the reason for discontinuation will be noted as "Adverse Event") or for another reason.

Withdrawn subjects will not be replaced.

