5.2.10 Classification of Subjects Who Discontinue the Study

For any subject who discontinues the study prior to completion, the most significant reason for early termination will be checked in the CRB. Reasons are listed below from the most significant to the least significant (refer to the CRB completion instructions for additional details and examples):

Adverse Event	To be used when the subject is permanently terminated from the study because of an AE (including an SAE), as defined in Section 9.1.1 .
Lost to Follow-up	To be used when the subject cannot be found or contacted in spite of efforts to locate him/her before the date of his/her planned last visit, as outlined in Section 5.2.9 . The certified letter was sent by the investigator and returned unsigned, and the subject did not give any other news and did not come to any following visit.
Protocol Deviation	To be used: 
 • In case of significant noncompliance with the protocol (e.g., deviation of the Inclusion/Exclusion criteria, non-compliance with time windows, blood sampling or vaccination refusal, missed injection, or error in the vaccine administration). • If the subject received the restricted treatments indicated in Section 6.7). • The subject signed the certified letter sent by the investigator but did not give any other news and did not come to any following visit.
Withdrawal by Subject	To be used: 
 • When the subject indicated unwillingness to continue in the study • When the subject made the decision to discontinue participation in the study for any personal reason other than an SAE/AE (e.g., subject is relocating, inform consent withdrawal, etc.)

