5.2.11 Follow-up of Discontinuations

The site should complete all scheduled safety follow-ups and contact any subject who has prematurely terminated the study because of an AE, a protocol deviation, or loss of eligibility.

For subjects where the reason for early termination was lost to follow-up or if the subject withdrew informed consent and specified that they do not want to be contacted again and it is documented in the source document, the site will not attempt to obtain further safety information.

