12.2.1 Full Analysis Set

The full analysis set (FAS) will include all randomized subjects who received at least one dose of the study vaccine and had a post-vaccination blood sample HAI result for at least one strain. Subjects will be analyzed according to the vaccine group to which they were randomized.

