12.2.3 Per-Protocol Analysis Set

The per-protocol analysis set (PPAS) is a subset of the FAS. The subjects presenting with at least one of the following relevant protocol deviations will be excluded from PPAS:

- Subject did not meet all protocol-specified inclusion criteria or met at least one of the protocol-specific exclusion criteria
- Subject did not receive vaccine
- Subject received a vaccine other than the one that he/she was randomized to receive
- Preparation and/or administration of vaccine was not done as per-protocol
- Subject did not provide the post-dose serology sample at V3 in the proper time window (i.e., 28 to 35 days after vaccination) or a post-dose serology sample (V3) was not drawn

Subject received a protocol-restricted therapy / medication / vaccine (prohibited therapies / medications / vaccines should have been indicated in [Section 6.7](#))

In addition to the criteria listed above, subjects will also be excluded from the PPAS if their HAI serology sample at V3 did not produce a valid test result for all strains.

The above protocol deviations leading to exclusion from the PPAS may be detailed and completed if necessary in the SAP, following the review of protocol deviations during the study conduct. In any case, the PPAS definition will be finalized before the database lock.

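### Automatic withdrawal for significant noncompliance can remove vaccinated subjects before the V3 sample, and so from the FAS as well as the PPAS

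*Protocol*

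**What the plan says.** Protocol 5.2.8 lists one cause under "The following will result in automatic withdrawal or exclusion of a subject from the study", namely "Significant noncompliance with the protocol, based on the Investigator's judgment". It adds: "Withdrawn subjects will not be replaced".

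Protocol 5.2.10 tells the site how to code the reason for early termination. Under Protocol Deviation it gives examples of significant noncompliance: deviation from the eligibility criteria, then "non-compliance with time windows, blood sampling or vaccination refusal, missed injection, or error in the vaccine administration". A separate bullet, without the word significant, begins "If the subject received the restricted treatments indicated in" and points to Section 6.7.

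Protocol 5.2.11 covers what happens next. For early terminations that arise from an adverse event, from lost eligibility or from a deviation, the rule is "The site should complete all scheduled safety follow-ups and contact any subject who has prematurely terminated the study". It does not mention the V3 blood sample.

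Protocol 12.2.1 and SAP 2.3.1 admit to the FAS only randomized, vaccinated subjects who "had a post-vaccination blood sample HAI result for at least one strain". Protocol 12.2.3 and SAP 2.3.2 define the PPAS as the FAS less subjects with listed deviations, for example "Subject received a vaccine other than the one that he/she was randomized to receive". Protocol 12.3.2 treats confirmation of the PPAS result by the FAS as a sufficient sensitivity analysis.

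**The concern.** The same kinds of event are handled in two ways that do not fit together. Under 5.2.8 and 5.2.10 an ineligible subject, a subject given the vaccine wrongly or a subject given a restricted treatment can be removed from the study. Under 12.2.3 the same subject is kept, gives a V3 sample, counts in the FAS and is left out of the PPAS only.

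If sites act on the withdrawal rule, and no sample is taken afterwards, the FAS loses the subjects whose inclusion is meant to distinguish it from the PPAS. Agreement between the two sets would then be partly built in.

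This matters more because 12.3.2 rests on data missing completely at random, arguing that a link between dropout and immune response is very unlikely. Withdrawal for a restricted treatment does not fit that argument. Section 6.7 restricts immunosuppressive therapy, immune globulins or blood products, and other vaccines, and the same section classes such agents as able to affect the immune response.

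Nothing is gained in exchange. The vaccine is one dose at V1, so withdrawing a vaccinated subject for a deviation prevents no further study dosing and only puts the Day 28 result at risk.

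**Working it through.** The plan states no power, margin or derived sample size, so there is no figure to reproduce. The check compares definitions, followed by arithmetic for scale.

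**Step 1: which examples in 5.2.10 can cost the FAS a subject**

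| Example in 5.2.10 | PPAS exclusion in 12.2.3? | Can withdrawal remove a subject who would otherwise be in the FAS? |
|---|---|---|
| Eligibility deviation | Yes | Yes, if vaccinated and withdrawn before V3 |
| Error in vaccine administration | Yes | Yes, if withdrawn before V3 |
| Restricted treatment | Yes | Yes, if withdrawn before V3 |
| V3 time window | Yes | Usually not: often known only when the late sample is taken |
| V2 time window | No | Yes, if judged significant |
| Refusal of the V3 blood sample | Yes (no sample) | No: there is no sample under any rule |
| Vaccination refusal, missed injection | Yes (no vaccine) | No: not vaccinated, so outside the FAS |

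Three examples therefore matter for the overlap: eligibility, administration error and restricted treatment.

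**Step 2: what follows withdrawal.** Withdrawal is not itself an FAS exclusion. The loss needs three conditions together: the subject was vaccinated, was withdrawn before V3, and gave no later sample. Section 5.2.11 settles safety follow-up and leaves the third condition open.

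**Step 3: scale**

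Inputs: 55 subjects per Cohort 2 group, 165 in total (Protocol 5.1.1); missing immunogenicity data expected to be at most 5% (Protocol 12.3.2). The number k lost per group through this rule is not in the documents; the range 1 to 5 is an assumption.

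- Expected missing data for any reason: 0.05 × 55 = 2.75 per group; 0.05 × 165 = 8.25 overall.
- If k of n outcomes are unknown, a group's seroconversion rate can lie anywhere in a range of width k/n. For the difference between two groups, each losing k, the width is 2k/n.

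| k per group (assumed) | One rate, k/55 | Difference, 2k/55 |
|---|---|---|
| 1 | 1.8 points | 3.6 points |
| 3 | 5.5 points | 10.9 points |
| 5 | 9.1 points | 18.2 points |

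- Precision, by the Newcombe-Wilson formula in SAP 2.5.8.4 with assumed rates of 50% in both groups. With n = 55 and z = 1.96, the Wilson limits are (2 × 55 × 0.5 + 3.84 ± 1.96 × √(3.84 + 4 × 55 × 0.25)) / (2 × (55 + 3.84)) = 0.372 and 0.628. The half-width is 1.96 × √(2 × 0.372 × 0.628 / 55) = 0.181, or 18.1 points. The same calculation gives 18.5 points with 52 per group and 18.9 with 50.

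Losing 3 per group adds 0.4 points to the half-width. The effect is on selection, not on precision.

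**The case against.** The strongest reply is that the protocol never waives the V3 sample. Section 5.1.3 says that all subjects give it, and 5.2.11 keeps terminated subjects in scheduled safety follow-up, which includes the V3 visit where the sample is due. This stands in part: the text is silent, and a reader who infers that the sample is cancelled goes too far. But 5.1.3 is the general schedule and treats blood sampling and safety data under separate headings, whereas 5.2.11 is the specific rule for discontinued subjects and names safety only. A site could reasonably read it either way.

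A reader might also infer that every deviation leads to withdrawal. It does not. The trigger is noncompliance judged significant, and 5.2.10 is a table for coding reasons, not a list of triggers. Other provisions expect subjects with deviations to remain: the PPAS is carved out of the FAS, SAP 2.2 lists subjects given an unallocated vaccine, and SAP Section 4 foresees a subject allocated to IM but injected SC. So the FAS need not shrink to the PPAS. These provisions also show that the analysis plan relies on retention that 5.2.8 does not secure.

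A third tempting inference is that the loss would differ by arm, because a wrong-route error with QIV-HD can occur only in the two QIV-HD groups. The documents do not support it. QIV-SD is assigned SC and could equally be given by the wrong route, and Protocol 6.4 blinds the Investigator in charge of safety assessment to vaccine and route.

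Finally, the study is descriptive and the main immunogenicity analysis uses the Cohort 2 PPAS, which already excludes most of these subjects. That is correct, and it limits the point to the sensitivity comparison.

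**Conclusion.** The point holds, within limits. Followed as written, 5.2.8 can withdraw vaccinated subjects for deviations that 12.2.3 means to handle by PPAS exclusion, and 5.2.11 does not secure their V3 sample. Any such subject without a post-vaccination HAI result is lost from the FAS too, which weakens the only sensitivity analysis that 12.3.2 offers.

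The size cannot be stated from the documents. It depends on how often Investigators judge a deviation significant before V3 and on whether sites still draw the sample. Three lost subjects per group, an assumed figure, would slightly exceed the 2.75 per group that the plan allows for all causes together. The main PPAS estimates would be little affected.

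**What to change.** - In Protocol 5.2.8, limit automatic withdrawal for noncompliance to the time before vaccination. Leave withdrawal at the subject's request and withdrawal for safety concerns as they are.
- In Protocol 5.2.11, state that a vaccinated subject with a protocol deviation stays in follow-up and is asked for the BL2 sample at V3, unless the subject withdraws consent or is withdrawn for safety. The deviation is recorded and handled by the PPAS exclusion rules.
- Keep the Protocol Deviation reason in 5.2.10, so that subjects who do terminate for this reason can still be coded.

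The FAS and PPAS definitions in the protocol and SAP need no change. The cost is a short protocol amendment and a site instruction. BL2 is already in the visit schedule, so no procedure is added.

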5.2.9 Lost to Follow-up Procedures

In the case of subjects who fail to return at V2 and/or V3, documented reasonable effort (i.e., documented telephone calls and certified mail) should be undertaken to locate or recall them, or at least to determine their health status while fully respecting their rights. These efforts should be documented in the CRB and in the source documents.

5.2.10 Classification of Subjects Who Discontinue the Study

For any subject who discontinues the study prior to completion, the most significant reason for early termination will be checked in the CRB. Reasons are listed below from the most significant to the least significant (refer to the CRB completion instructions for additional details and examples):

Adverse Event	To be used when the subject is permanently terminated from the study because of an AE (including an SAE), as defined in Section 9.1.1 .
Lost to Follow-up	To be used when the subject cannot be found or contacted in spite of efforts to locate him/her before the date of his/her planned last visit, as outlined in Section 5.2.9 . The certified letter was sent by the investigator and returned unsigned, and the subject did not give any other news and did not come to any following visit.
Protocol Deviation	To be used: 
 • In case of significant noncompliance with the protocol (e.g., deviation of the Inclusion/Exclusion criteria, non-compliance with time windows, blood sampling or vaccination refusal, missed injection, or error in the vaccine administration). • If the subject received the restricted treatments indicated in Section 6.7). • The subject signed the certified letter sent by the investigator but did not give any other news and did not come to any following visit.
Withdrawal by Subject	To be used: 
 • When the subject indicated unwillingness to continue in the study • When the subject made the decision to discontinue participation in the study for any personal reason other than an SAE/AE (e.g., subject is relocating, inform consent withdrawal, etc.)

5.2.11 Follow-up of Discontinuations

The site should complete all scheduled safety follow-ups and contact any subject who has prematurely terminated the study because of an AE, a protocol deviation, or loss of eligibility.

For subjects where the reason for early termination was lost to follow-up or if the subject withdrew informed consent and specified that they do not want to be contacted again and it is documented in the source document, the site will not attempt to obtain further safety information.

5.3 SAFETY EMERGENCY CALL

If, as per the Investigator's judgment, a subject experiences a medical emergency, the Investigator may contact the Sponsor for advice on study related medical question or problem. If the Sponsor is not available, then the Investigator may contact the Call Center - available 24 hours a day, 7 days a week - that will forward all safety emergency calls to the appropriate primary or back-up Sponsor's contact, as needed. The toll-free contact information for the Call Center is provided in the clinical study protocol (see Names and addresses).

This process does not replace the need to report an SAE. The investigator/Sub-investigator is still required to follow the protocol defined process for reporting SAEs to the Sponsor (see [Section 10](#)).

5.4 MODIFICATION OF THE STUDY AND PROTOCOL

All appendices attached hereto and referred to herein are made part of this clinical study protocol.

The Investigator should not implement any deviation from, or changes of the clinical study protocol without agreement by the Sponsor and prior review and documented approval/favorable opinion from the IEC/IRB and/or notification/approval of health authorities (competent regulatory authority) of an amendment, as required by local regulation, except where necessary to eliminate an immediate hazard(s) to clinical study subjects, or when the change(s) involves only logistical or administrative aspects of the study. Any change agreed upon will be recorded in writing, the written amendment will be signed by the Investigator and by the Sponsor and the signed amendment will be filed with this clinical study protocol.

Any amendment to the clinical study protocol requires written approval/favorable opinion by the IEC/IRB prior to its implementation, unless there are overriding safety reasons.

In case of substantial amendment to the clinical study protocol, approval from the health authorities (competent regulatory authority) will be sought before implementation.

In some instances, an amendment may require a change to the ICF. The Investigator must receive an IEC/IRB approval/favorable opinion concerning the revised ICF prior to implementation of the change and subject signature should be re-collected if necessary.

